**Figure 3.1. Study Schema**

### 3.2 Determination of Sample Size

Approximately 15 subjects will be enrolled including approximately 5 subjects with hydrops fetalis. Subjects under the age of 5 years at the time of informed consent with a confirmed diagnosis of MPS 7 will be enrolled. Additional subjects previously treated with UX003 under an emergency IND or similar process may also be enrolled at the discretion of the Sponsor. Due to the extremely low prevalence of the disease, the sample size is primarily based on the ability to find eligible subjects.

### 3.3 Interim Analysis

Analyses may be performed at any time during the study at the discretion of the Sponsor. There is no unblinding during these analyses since it is an open-label study.

### 3.4 Data Monitoring Committee

Safety will be monitored by Ultragenyx on a continual basis. An independent data monitoring committee will not be used.

### 3.5 Randomization and Blinding Method of Assigning Subjects to Treatment Groups

Not applicable. This is an open label study without randomization of treatment assignment.

## 4 STUDY CLINICAL OUTCOMES AND COVARIATES

All data are collected according to the schedule of assessments included in the protocol.

### 4.1 Primary Efficacy Variable

- Urinary GAG Excretion: First morning void urine will be evaluated for uGAG concentration and normalized to urinary creatinine concentration.

### 4.2 Secondary Efficacy Variables

- Growth will be assessed by anthropometric measurements including standing height (length or sitting height as applicable), head circumference, and weight. Growth velocity will be calculated and compared with pre-treatment growth velocity when available and published normative data for age and gender.
- Hepatosplenomegaly: The volume of the liver and spleen will be determined using ultrasound. If an ultrasound is not possible, the liver and spleen should be assessed by physical exam. Ascites will also be assessed.

### 4.3 Tertiary Efficacy Variables

- Additional GAG measures including serum GAG and supplementary uGAG assays
- Clinical Global Impression Scale: Physicians caring for each subject will provide a global assessment of change using a seven point scale ranging from -3 (severe worsening) to +3 (significant improvement). The Clinical Global Impression (CGI) scale will be supported by reported changes in a list of disease-specific abnormalities projected to respond to treatment.
- Functional Development will be assessed by the Bayley Scales of Infant and Toddler Development® – Third Edition (Bayley-III).
- Motor Functioning will be assessed by a gross motor development milestone checklist.
- Cardiac Ventricular Mass: Ventricular mass will be assessed by echocardiogram (ECHO). Valvular and cardiac function may also be evaluated.
- Pulmonary Function: Pulse oximetry will be used to assess respiratory difficulties; resting O2 saturation will be measured while the subject is breathing room air.
- Biochemical Markers of Bone Turnover (BTMs): Levels of serum markers of bone formation and bone resorption will be measured.

### 4.4 Safety Assessments

Safety will be evaluated by the incidence and frequency of adverse events (AEs) and serious adverse events (SAEs), including clinically significant changes from study baseline to scheduled time points in:

- Vital signs and weight
- Physical examination findings
- Clinical laboratory evaluations
- Concomitant medications
- Antibodies to rhGUS
- Complement C3, C4 and CH50 levels (if indicated to characterize the immune response following a drug related IAR)

## 5 DEFINITIONS

### 5.1 Baseline

- uGAG baseline is defined as the average of all study assessments prior to or on the date of initiation of treatment with UX003 in this study. For subject(s) previously treated with UX003 under an emergency IND, initial baseline will be derived as the average of all assessments prior to or on the date of initiation of the initial treatment with UX003.
- Baseline for growth measurement is defined as the last non-missing study assessment prior to the first dose of UX003. For subject(s) previously treated with UX003 under an emergency IND, the last assessment prior to the initial UX003 treatment may also be used.
- The baseline for echocardiogram: ECHO performed within three months prior to baseline visit may be used as baseline provided cardiac ventricular mass can be calculated.
- Baseline value for other endpoints is the last non-missing study assessment prior to the first dose of UX003 in this study unless otherwise specified.

### 5.2 Fold Increase in uGAG Above Upper Normal Limit

The fold increase in uGAG above upper limit of normal is the ratio of the uGAG value over the uGAG upper limit of normal. If the ratio is less than 1, then it is set as 1.

### 5.3 Growth

Growth will be assessed by anthropometric measurements. Z-scores and percentiles will be calculated using CDC growth chart ([Kuczmarski, 2000](#)).

Growth velocity of standing height (cm or Z score) may be assessed by a model-based approach. A linear regression model for each subject will be built for selected pre-treatment (eg., within 2 years prior to Baseline) data and post-treatment data:

$$Y_t = \beta_0 + \beta_1 X_t + \varepsilon_i$$

Where  $Y_t$  is the standing height (cm) or Z score based on the standing height measured at Time t;  $X_t$  is the time when standing height is measured;  $\beta_0$  is the intercept,  $\beta_1$  is the slope of the regression model;  $\varepsilon_i$  is random error term.

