## 7 INVESTIGATIONAL PLAN

### 7.1 Overall Study Design and Plan

UX003-CL203 is an open-label, multicenter, Phase 2 study to assess the safety and efficacy of UX003 in pediatric MPS 7 subjects. The study seeks to enroll approximately 15 subjects less than 5 years of age at the time of informed consent, and will attempt to include approximately 5 infants with hydrops fetalis if possible. Subjects with prior exposure to UX003 treatment under an emergency IND may also be enrolled at the discretion of the Sponsor. In the initial 48 weeks of treatment, subjects will receive UX003 via IV infusion at a dose of 4 mg/kg QOW. Subjects who complete the 48-week study may choose to continue UX003 treatment in the Continuation Period up to 240 weeks, or until the subject withdraws consent, the subject is discontinued from the study at the discretion of the Investigator or Ultragenyx, or the study is terminated. Figure 7.1.1 provides a schematic of the overall study design.

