#### **7.3.1 Inclusion Criteria**

Individuals eligible to participate in this study must meet all of the following criteria:

1. Confirmed diagnosis of MPS 7 based on leukocyte or fibroblast glucuronidase enzyme assay, or genetic testing
2. Under 5 years of age at the time of informed consent
3. Written informed consent of Legally Authorized Representative after the nature of the study has been explained, and prior to any research-related procedures

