##### **7.5.2.3.3 Functional Development**

Functional Development will be assessed by the Bayley Scales of Infant and Toddler Development – Third Edition (Bayley-III). The instrument will be administered at Baseline (Week 0), and at the Week 24 and 48 (or Early Termination) study visits. During the

Continuation Period, the Bayley-III will be completed at 48-week intervals. Bayley-III will not be performed at the ET visit if the assessment was conducted within 1 month of termination.

The Bayley-III ([Bayley 2006](#)) is a standard series of measurements developed to assess the motor (fine and gross), language (receptive and expressive), and cognitive development of infants and toddlers, aged 1 month - 42 months. This measure consists of a series of developmental play tasks and takes between 45 - 60 minutes to administer. The total raw score will be converted into a scaled score and a composite score with percentile rank to compare performance to healthy same-age peers. Unless a child has achieved the highest raw score on the test, the Bayley-III assessments will continue throughout the study to monitor the progress of a child. Additionally, if valid and reliable administration of the instrument is not possible based on the clinical judgment of the Investigator, e.g. language difficulties or clinical condition of the subject, testing may be omitted at that visit.

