#### **7.5.4.1 Medical History**

A complete medical history will be obtained at the Screening visit. At the Baseline visit, any changes in medical history since Screening will be recorded. General medical information includes subject demographics (date of birth, ethnicity, and sex) and a history of major medical illnesses, diagnoses, and surgeries. Growth history for height and weight will be collected. Pretreatment measurements of height and weight should be collected from the records if possible to assure a pre and post treatment growth rate can be assessed. MPS7 treatment history and relevant concomitant medications will be recorded (start date, stop date, dose, dose regimen). Medications include prescription, over-the-counter, herbal and nutritional supplements. Any relevant concomitant therapy, including physical/occupational therapy will be recorded.

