## **Missing Medical History Related Dates (eg, diagnosis date) or Birth Date**

- If only the day is missing, impute the day to first day of the month.
- If day and month are missing, impute to January
- If year is missing, then no imputation will be done, the date will be missing.

If the imputed medical history related date is earlier than birth date, then birth date will be used.

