### 8.3 Demographics and Other Baseline Characteristics

Demographic parameters (e.g., age, sex, race and ethnicity) and other baseline characteristics (i.e., initial diagnosis, height and weight) assessed at baseline will be summarized and listed.

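### Neither document specifies gestational age or the age basis for growth z-scores and Bayley-III, so a preterm infant enrolled in early infancy can show a spurious z-score rise

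*SAP*

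**What the plan says.** On growth, SAP 5.3 states that "Z-scores and percentiles will be calculated using CDC growth chart". It gives no rule for which age enters the chart. SAP 8.7.2 summarises change from baseline in anthropometric measurements by visit, lists z-scores and percentiles, and presents growth velocity before and after treatment. Both documents also plan a comparison of growth with published norms for age and gender (protocol 7.6.5, SAP 4.2). The regression slope in SAP 5.3 is optional and is written for standing height, in cm or as a z-score.

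On development, protocol 7.5.2.3.3 says the Bayley-III raw score is "converted into a scaled score and a composite score with percentile rank to compare performance to healthy same-age peers". SAP 8.7.3 summarises change in Bayley-III scores by visit.

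On what is recorded about birth, protocol 7.5.4.1 says "General medical information includes subject demographics (date of birth, ethnicity, and sex) and a history of major medical illnesses, diagnoses, and surgeries". In SAP 8.3, beyond demographic parameters, "other baseline characteristics (i.e., initial diagnosis, height and weight) assessed at baseline will be summarized and listed". Gestational age, prematurity and birth size appear in neither document.

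On who is enrolled, the age criterion is "Under 5 years of age at the time of informed consent", with no lower limit, and the study "will attempt to include approximately 5 infants with hydrops fetalis if possible" among about 15 children.

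On incomplete birth dates, SAP 7.2 says "If only the day is missing, impute the day to first day of the month" and "If day and month are missing, impute to January".

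**The concern.** A child born several weeks early is developmentally younger than the calendar says. Read against a chart at chronological age, the child looks too small. The shortfall in centimetres is the growth expected over the missing weeks, so it is large when growth is fast (the first months) and shrinks as growth slows. A child who follows the median for corrected age throughout therefore starts with a low z-score and climbs towards zero over 48 weeks.

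Growth velocity is part of the secondary objective, and no untreated arm would show the same climb. With about 15 subjects, individual listings will carry much of the interpretation, so a rise of about 1 SD in one infant would be noticed. The same open question of age basis reaches Bayley-III standard scores, which are referenced to age.

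The birth-date rule is a separate and smaller matter. Both imputations pick the earliest possible date, so the age they produce is correct or too high, never too low.

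**Working it through.** The documents give no figure for this point, so there is nothing to reproduce. The size has to be illustrated with assumed growth values; none of those below come from the documents.

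**Formula.** For a child on the median for corrected age, z error at age a = [M(a − d) − M(a)] / SD(a), where M is median length, d is months born early and a is chronological age. Week 48 is 48 × 7 / 30.44 = 11.04 months after entry. Four weeks is 28 / 30.44 = 0.92 month.

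**Check 1: constant velocities.** Assume 3.5 cm/month and SD 2.2 cm at entry (about 1.5 months of age), and 1.2 cm/month and SD 2.5 cm at Week 48. For birth 4 weeks early:
- Entry: −(0.92 × 3.5) / 2.2 = −3.22 / 2.2 = −1.46
- Week 48: −(0.92 × 1.2) / 2.5 = −1.10 / 2.5 = −0.44
- Spurious rise: 1.46 − 0.44 = about +1.0 SD

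**Check 2: a full curve.** Assume median length of 50 cm at birth, 57.7 at 2 months, 66.5 at 6, 75 at 12, 87 at 24 and 102.5 at 48, interpolated, with SD 3.7% of the median. For birth at 36 weeks and entry at 2 months:
- Entry: (54.60 − 57.70) / 2.135 = −1.45
- Week 48 (13.04 months): (75.14 − 76.23) / 2.82 = about −0.38
- Spurious rise: 1.45 − 0.38 = +1.07

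Spurious rise by age at entry (range with SD varied by ±15% in brackets):

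| Entry age | Born at 36 weeks | Born at 32 weeks |
|---|---|---|
| 2 months | 1.07 (0.93 to 1.26) | 2.51 (2.18 to 2.96) |
| 6 months | 0.35 (0.30 to 0.41) | 0.75 (0.65 to 0.88) |
| 12 months | 0.17 (0.15 to 0.20) | 0.35 (0.31 to 0.41) |
| 24 months | 0.07 (0.06 to 0.08) | 0.14 (0.12 to 0.17) |
| 48 months | 0.02 (0.01 to 0.02) | 0.03 (0.03 to 0.04) |

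On corrected age the error is zero at every visit by construction of the model.

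**Direction in the velocity comparison.** The spurious climb is steepest soonest after birth, which is before treatment. Slopes were fitted to the error curve from birth to entry and from entry to Week 48, with entry at 6 months:
- Born at 32 weeks: about +5.1 z/year before treatment and +0.8 z/year after
- Born at 36 weeks: about +2.4 and +0.4 z/year

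The pre-treatment slope is inflated more, so this comparison is biased against the drug.

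**Birth-date rule.** A missing day set to the first overstates age by 0 to 30 days, about half a month on average. With the values of Check 1, the z error is −(0.5 × 3.5) / 2.2 = −0.80 at entry and −(0.5 × 1.2) / 2.5 = −0.24 at Week 48, a spurious rise of about 0.56 SD in a young infant. A missing month set to January can overstate age by up to about 11 months or more. Either applies only if a birth date is in fact incomplete.

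**The case against.** A reader might infer that gestational age is not collected at all. The documents do not show that. Protocol 7.5.4.1 asks for a complete medical history, its list is introduced as inclusive, and neither the CRF nor the Study Reference Manual is available here. What can be said is that gestational age is not specified.

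A reader might also infer that growth results are generally biased in the drug's favour. That is too strong, for four reasons, all of which stand:
- In the pre/post z-velocity comparison the bias runs the other way.
- SAP 8.7.2 lists z-scores and does not clearly commit to summarising their mean change. The optional slope uses standing height, which infants measured by length would not supply.
- The effect depends on age at entry and weeks early. Most of the eligible age range is little affected.
- Nothing in the documents gives a rate of preterm birth or ties hydrops to preterm delivery, so no shift in the group mean can be claimed.

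It is also fair that a missing birth day is unlikely in a trial infant, since date of birth is collected and decides eligibility. For Bayley-III, a tertiary measure, SAP 8.7.3 does not say whether raw or standard scores are summarised; raw scores do not depend on age, and no size is calculated here.

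These points narrow the concern without removing it. Comparison with norms for age is planned and cannot be done without choosing an age basis. One unstated choice moves two growth readouts in opposite directions, and it would otherwise be made with open-label data in hand.

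**Conclusion.** The concern holds in a limited form: the plan leaves the age basis for growth z-scores and Bayley-III standard scores unstated and does not specify recording the variable needed to correct it. For a child born 4 weeks early and enrolled at 1.5 to 2 months, the spurious rise over 48 weeks is about +1.0 to +1.1 SD. It is about +0.35 for entry at 6 months, under 0.2 at 12 months and near zero from 2 years; earlier birth makes it larger. It favours the drug in within-child z change from baseline and counts against it in pre/post z-velocity.

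These sizes rest on assumed length curves and SDs and on a child who tracks the median for corrected age. True growth failure from disease could hide the rise. How many subjects this touches is unknown and may be none.

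The birth-date rule in SAP 7.2 is one-sided as written, though it may rarely be used. Both matters are worth correcting because the remedy is cheap.

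**What to change.** - Protocol 7.5.4.1: add gestational age at birth to the medical history, taken from existing records.
- SAP 5.3 and 8.7.3: state that gestation-corrected age is used up to a stated age (24 months is one workable cut-off) for growth z-scores, normative growth comparisons and Bayley-III standard scores.
- SAP 7.2: impute a missing birth day to mid-month, and compute no age-standardised score when the birth month is unknown.

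The cost is one CRF field and a few sentences of SAP text, with no extra procedure for any child. The downside for the sponsor is that some apparent catch-up growth may shrink.

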#### **5.4 Anti-rhGUS Antibody Titer Values**

Subject sera will be tested using a bridging anti-drug antibody (ADA) ELISA to screen for antibodies to rhGUS. Samples which are positive in the confirmation assay will then be tested in the titer assay giving a titer value, and also be tested with the neutralizing antibody assay (NAb).

#### **5.5 Duration of Exposure to UX003**

Duration of exposure to UX003 in days in this study is defined as: last date of UX003 infusion minus first date of UX003 infusion in this study + 14 days

### **6 ANALYSIS POPULATIONS**

#### **6.1 Full Analysis Set**

The full analysis set is defined as all enrolled subjects who received at least 1 dose of UX003 during the study.

### **7 DATA SCREENING AND ACCEPTANCE**

#### **7.1 Handling of Missing and Incomplete Data**

Missing clinical outcome data can occur for multiple reasons, including missed subject visits and measures with missing item scores. Missing and incomplete data will be identified through a review of tables and listings for this study. Missing and incomplete data will be identified for investigation, and possible resolution, by Data Management prior to the study database lock.

In general, missing data will be treated as missing, unless otherwise specified. When a change from baseline is assessed, only subjects with a baseline and at least one post-baseline measurement will be included in the analysis.

#### **7.2 Missing Date Imputation Rules**

For scheduled visit, the visit number will be used for analyses and the missing date will not be imputed.

#### **Missing Date of the Last Dose of Investigational Product**

When the date of the last dose of investigational product is missing for a subject, all efforts should be made to obtain the date from the Investigator. If after all efforts are made it is still missing, the last visit date will be used as the last dose date.

## **Missing Medical History Related Dates (eg, diagnosis date) or Birth Date**

- If only the day is missing, impute the day to first day of the month.
- If day and month are missing, impute to January
- If year is missing, then no imputation will be done, the date will be missing.

If the imputed medical history related date is earlier than birth date, then birth date will be used.

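### If a birth date is incomplete, the SAP's earliest-date rule makes the child's age too old, which distorts CDC growth z-scores in the first months of life (minor correction)

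*SAP*

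**What the plan says.** The relevant rule in SAP 7.2 is headed "Missing Medical History Related Dates (eg, diagnosis date) or Birth Date", so birth date and history dates share one convention. It has three steps: "If only the day is missing, impute the day to first day of the month"; "If day and month are missing, impute to January"; and "If year is missing, then no imputation will be done, the date will be missing". For January the day is not stated; I take it as the 1st.

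Age enters the growth analysis through SAP 5.3: "Z-scores and percentiles will be calculated using CDC growth chart". The SAP does not say how age is derived for this. SAP 8.7.2 lists the z-scores and percentiles, summarises change from baseline in anthropometric measurements by visit (without saying whether z-scores are among them), and presents growth velocity before and after treatment. SAP 5.3 allows velocity to be modelled by a per-subject regression, in cm or in z.

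Protocol 7.5.4.1 collects date of birth as a demographic item. Neither document reports an incomplete birth date. Neither plans a flag or a sensitivity analysis for subjects whose birth date is imputed.

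**The concern.** For a diagnosis date, taking the earliest possible day is a harmless convention. For a birth date it is a one-sided error in age, and age is an input to a secondary efficacy measure. A fixed overstatement of age compares the child with an older, longer reference child. The gap is widest when growth is fastest and narrows as growth slows, so the z-score drifts upward with no true change.

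The study seeks about 5 infants with hydrops fetalis among about 15 children, so the sensitive age range is a planned part of the sample. There is a single arm, and with so few children one affected infant could be visible in a summary. The neighbouring rules in SAP 7.2 are more careful. The last-dose rule requires efforts to obtain the date first, and the rule for adverse-event and medication start dates uses the first-dose date to limit the result. The birth-date rule does neither.

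**Working it through.** The plan states no figure for this error, so there is none to reproduce. The CDC tables are not in the documents, so every z-score size below rests on assumed growth curves.

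**Step 1. Error in age.** Age error = true birth date − imputed birth date. I enumerated all 1,826 birth dates from 2011 to 2015.

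| Missing | Error in age (days too old) | Mean | No error |
|---|---|---|---|
| Day | 0 to 30 | 14.7 | 3.3% (born on the 1st) |
| Day and month (1 January assumed) | 0 to 365 | 182 | born on 1 January |

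The error is never negative.

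**Step 2. One infant by hand.** With a constant SD, the z error = −[M(age + error) − M(age)] / SD, where M is median length. Assume M = 54 cm at 1 month, 57.5 at 2, 75.5 at 12 and 82 at 18, linear between, and SD 2 to 3 cm. The error is 14.7 days, or 14.7/30.44 = 0.483 month.

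- Baseline at 1 month: growth is 3.5 cm/month, so M is overstated by 3.5 × 0.483 = 1.69 cm. The z error is −1.69/2 = −0.85 to −1.69/3 = −0.56.
- Week 48, 336 days later, at 12.04 months: growth is (82 − 75.5)/6 = 1.083 cm/month, so M is overstated by 1.083 × 0.483 = 0.52 cm. The z error is −0.26 to −0.17.
- Spurious rise: (1.69 − 0.52)/SD = 1.17/2 to 1.17/3, or about +0.6 to +0.4 SD.

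**Step 3. Range over curves.** This used three concave length curves (50 cm at birth, 74–76 at 12 months, 86–88 at 24, 95–96 at 36). The SD was 2.0 cm, 3.5 cm, or rising from 2.2 to 4.5 cm. True z was held constant at 0 or −2.

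| Age at Baseline | 48-week rise in z, 14.7-day error | 48-week rise in z, 30-day error |
|---|---|---|
| 0.5 month | +0.28 to +0.84 | +0.55 to +1.64 |
| 3 months | +0.17 to +0.36 | +0.32 to +0.67 |
| 6 months | +0.09 to +0.17 | +0.19 to +0.35 |
| 12 months | +0.04 to +0.10 | – |
| 24 months | +0.02 to +0.04 | – |
| 36 months | +0.01 to +0.02 | – |

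At 0.5 month, the Baseline z error for the mean shift is −0.45 to −1.11. With the month also missing (182 days), the rise is +0.8 to +1.7 at 6 months and +0.5 to +1.1 at 12 months.

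**Step 4. Velocity.** A constant shift in age leaves a slope in cm unchanged. For the slope in z I used one curve and SD pair and the 14.7-day error:

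| Age at Baseline | Spurious pre slope (z/year) | Spurious post slope (z/year) | Post − pre |
|---|---|---|---|
| 6 months | +1.28 | +0.18 | −1.09 (from unrounded slopes) |
| 12 months | +0.66 | +0.10 | −0.56 |

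The artefact is larger before treatment, so the before-and-after contrast is biased downward although the post-treatment slope alone is biased upward.

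**The case against.** The strongest reply is that the rule may never fire. Date of birth is collected, the inclusion criterion is "Under 5 years of age at the time of informed consent", Protocol 7.5 requires eligibility to be confirmed before treatment, and SAP 7.1 sends incomplete data to Data Management before lock. With about 15 children at 2 to 6 sites, incomplete birth dates should be uncommon. This stands, and it is why the point is minor. It does not remove the point: the SAP itself provides for an incomplete birth date, and under 5 years can often be confirmed without the exact day.

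The route to a reported result is also narrow. SAP 8.7.2 lists z-scores but does not expressly summarise their change. The z-slope model is optional and names standing height, which the youngest infants are unlikely to have. Growth is descriptive, and SAP 8.1 puts all raw and derived data in listings or graphs. All of this stands.

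The earliest-date convention has one merit: an imputed birth never falls after a true dated event, and SAP 7.2 uses birth date as the floor for other imputed dates. Bounding the midpoint by the child's earliest dated record keeps the first property. Some imputed history or medication dates in the birth month would move to the later birth date, which is a small cost.

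A reader might infer that the rule favours the drug on growth overall. Step 4 contradicts this for z-velocity before versus after treatment, and cm measures do not move. A reader might also infer that a child near 5 could be imputed as over age. That changes no analysis, because the full analysis set in SAP 6.1 has no age condition. Finally, Protocol 7.5.2.3.3 converts Bayley-III scores to a "percentile rank to compare performance to healthy same-age peers", but neither document says the imputed birth date is used for that, so no effect is shown.

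**Conclusion.** The rule is unsuitable for birth dates, but the point is a minor correction. If a birth date is incomplete, the imputed age is too old unless the child was born on the 1st (or on 1 January when the month is also missing). With only the day missing, this matters mainly in the first months of life: a spurious 48-week rise in length z of about +0.3 to +0.8 SD at 0.5 month and +0.2 to +0.4 at 3 months, falling to at most 0.1 from 12 months on (mean error). Change from baseline in z and the post-treatment z slope are biased upward, and the z-velocity contrast before versus after treatment downward. Change and velocity in cm are unaffected.

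The direction and size of the age error follow from the rule, with 1 January assumed where the month is missing. The z-score sizes depend on assumed curves and SDs. The documents do not support saying that infant z-scores in this trial are biased in general: with complete birth dates there is no effect.

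**What to change.** Take birth date out of the shared rule in SAP 7.2 and give it its own:

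- If only the day is missing, impute the midpoint of the possible dates in that month, bounded above by the child's earliest dated record (first measurement or consent). Using the 15th without the bound, the age error becomes −14 to +16 days with mean +0.7, against 0 to +30 with mean 14.7 now.
- If the month is missing, derive no z-scores or percentiles until the site supplies the birth month or the age in days; list the raw values. A mid-year date would centre the error but leave up to about six months either way, which is too much for one infant.
- Flag every subject with an imputed birth date in the growth listings.
- Keep the first-of-month rule for diagnosis and other history dates.

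The cost is a few sentences in the SAP. The small downside is that a child with no known birth month has no z-score.
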